## **3. Sample size**

The primary outcome for DISC is the score obtained for the 11 items in part two of the PEM at 12 months post treatment. Previous survey data collected from a representative sample of 880 patients with Dupuytren's Contracture showed the standard deviation of the scores for the 11 items in part 2 of

the PEM at baseline to be 22 points (unpublished). We estimate that a 6 point difference on the PEM at 12 months post-treatment is the threshold at which differences become relevant to the patient, and represents an appropriate non-inferiority margin. An effective sample size of 568 participants (284 per arm) is required to obtain 90% power to assess non-inferiority of collagenase based on the upper limit of a two sided 95% confidence interval (CI) (equivalent to a one-sided 97.5% CI) for the treatment difference ( $\delta = \text{collagenase} - \text{surgery}$ ) at 12 months post treatment, assuming a non-inferiority margin of 6 points and a standard deviation of 22 points. This calculation is based upon the sample size needed for 90% power in a one-sided independent samples t-test of size 2.5%, of  $H_0: \delta \geq 6$  vs  $H_1: \delta < 6$ , ignoring informative baseline covariates (reference joint and baseline PEM score). If  $\delta = 6$ , then we would expect the null hypothesis that collagenase is inferior to surgery to be rejected in 2.5% of hypothetical repetitions of the trial. If  $\delta = 0$ , then we would expect the null hypothesis that collagenase is inferior to surgery to be (correctly) rejected in 90% of hypothetical repetitions of the trial (assuming an analysis based on a one sided independent samples t-test of size 2.5%). Assuming 20% attrition at the 12 month follow up, the total target sample size is 710.

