#### **4. Randomisation**

The randomisation sequence was designed by the study statistician and is accessed via telephone or the internet using a secure, central randomisation service hosted by Sealed Envelope Ltd. This will ensure adequate allocation concealment for the study. This service will record information to identify all potential participants and their eligibility to avoid inappropriate entry of patients into the trial. The research team at each study site will access the system to complete randomisation following participant consent and completion of baseline assessments. Access to the system for representatives at individual sites will be coordinated and controlled by the trial project team at YTU. Both participants and clinicians will not be blind to allocation. The randomisation system has been designed to allocate participants 1:1 to each of the two study treatment arms. The system uses block randomisation with randomly varying block sizes, stratified by reference joint (MCP or PIP). The actual allocation sequence has been generated using a randomly generated seed provided by a statistician not involved in the ongoing or final analysis of the study.

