Further treatment	Binary	No further treatment = 0, Further treatment = 1. Defined as additional treatment to the reference digit with collagenase, limited fasciectomy, dermofasciectomy or percutaneous needle fasciotomy	Logistic regression (with data augmentation if necessary)

The length of burn in will be determined by examining the trace plots of the chained equations algorithm, with a minimum burn in of 10 iterations being used if this appears to be sufficiently many for the algorithm to reach a stable state for all imputed variables. Imputed datasets will be analysed using the same model used for the primary analysis (without the Kenward-Roger degrees of freedom adjustment) with parameter estimates being combined according to Rubin's rules. The results will be reported in a similar manner to the reporting of the primary analysis results (Appendix E-2)

We will also investigate the sensitivity of results to departures from missing at random by imputing missing primary outcome data under a range of missing not at random scenarios. This will follow a pattern mixture modelling approach as implemented in the user contributed Stata command `rctmiss` [10]. At present this command does not support the covariance pattern model used for the primary analysis. We will therefore only use the outcome data from the 12 month post-treatment time point and use a substantive analysis based on analysis of covariance. Two versions of this analysis will be conducted; one including only patients who did not withdraw prior to treatment, and one including all randomised patients. The substantive analysis models will include allocation, study reference joint and baseline PEM score as predictors, with clustering by centre accounted for using a cluster robust standard error. Imputation will be performed allowing the sensitivity parameter of the pattern mixture model to vary from 0 (mean score among those with missing outcome data is the same as the mean score among those with non-missing outcome data, conditional on the covariates) to +/-10 (mean score among those with missing outcome data is +/-10 points larger/smaller than among those with non-missing outcome data, conditional on the covariates) in each group separately and across both groups. The tabular and graphical summaries used to report the results of these sensitivity analysis are given in Appendix E-2.

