## Appendix E-2 – Primary Outcome Reporting

**Table xx:** Descriptive summaries of PEM scores over time

	Collagenase (N = )	Surgery (N = )	Total (N = )
Baseline			
N			
Mean (SD)			
Median (Q1, Q3)			
Min, Max			
Pre-treatment			
N			
Mean (SD)			
Median (Q1, Q3)			
Min, Max			
Month 3			
N			
Mean (SD)			
Median (Q1, Q3)			
Min, Max			
Month 6			
N			
Mean (SD)			
Median (Q1, Q3)			
Min, Max			
Month 12			
N			
Mean (SD)			
Median (Q1, Q3)			
Min, Max			
Month 24			
N			
Mean (SD)			
Median (Q1, Q3)			
Min, Max			

**Table xx:** Estimated differences in mean PEM scores over time for each of the planned analyses of the primary outcome (except the analyses exploring sensitivity to outcome data being missing not at random)

	Estimated difference (95% CI)
Unadjusted analysis	
Baseline	-
Pre-Treatment	
3 Months	
6 Months	
12 Months	
24 Months	
Primary analysis	
3 Months	
6 Months	
12 Months (primary endpoint)	
24 Months	
Sensitivity analysis including baseline predictors of missingness	
3 Months	
6 Months	
12 Months	
24 Months	
Sensitivity analysis using multiply imputed data	
3 Months	
6 Months	
12 Months	

24 Months	
Sensitivity analysis adjusting for treatment delivery measurement	
3 Months	
6 Months	
12 Months	
24 Months	
Sensitivity analysis using data collected within planned follow up window*	
3 Months	
6 Months	
12 Months	
24 Months	
Sensitivity analysis adjusting for diathesis	
3 Months	
6 Months	
12 Months	
24 Months	
Complier Averaged Causal Effect Analysis	
12 Months	
Subgroup analysis	
Received preferred treatment	
Did not receive preferred treatment	
No treatment preference	

\*The specified timeframes are as follows. Pre-treatment PEM completed within 18 weeks of randomisation, month 3 and month 6 PEM completed within +/-14 days of 3 and 6 months post treatment, month 12 and month 24 PEM completed within +/- 3 months of 12 and 24 months post treatment.

**Table xx:** Sensitivity analysis exploring departures from MAR.

$\Delta$ (sensitivity parameter)	Imputing assuming $\Delta = \delta$ in which arm?	Estimated Difference (95% CI)
$\delta = 0$	Collagenase arm only	
	Surgery arm only	
	Both arms	
$\delta = 1$	Collagenase arm only	
	Surgery arm only	
	Both arms	
$\delta = 2$	Collagenase arm only	
	Surgery arm only	
	Both arms	
$\delta = 3$	Collagenase arm only	
	Surgery arm only	
	Both arms	
$\delta = 4$	Collagenase arm only	

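### The missing-not-at-random grid never shifts the two arms in opposite directions, so it omits the least favourable case for non-inferiority within its own ±10 range

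*SAP*

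**What the plan says.** Section 8.3.1 plans a pattern-mixture analysis of the 12-month PEM score using `rctmiss`. It has two versions: one restricted to patients who did not withdraw before treatment, and one with all randomised patients. The sensitivity parameter is the mean gap between missing and observed scores given the covariates. It runs from 0 to ±10 points, applied "in each group separately and across both groups".

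The Appendix E-2 table titled "Sensitivity analysis exploring departures from MAR" shows what this means in practice. Each block carries one value from -10 to 10 and has three rows: collagenase arm only, surgery arm only, both arms. With 20 non-zero values times 3 rows, plus the common zero case, there are 61 distinct scenarios. None gives the arms different non-zero values or opposite signs.

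The design figures are in section 3, "assuming a non-inferiority margin of 6 points and a standard deviation of 22 points". It states that "An effective sample size of 568 participants (284 per arm) is required to obtain 90% power", and then: "Assuming 20% attrition at the 12 month follow up, the total target sample size is 710". The opening of section 8 bases the decision mainly on whether the upper limit of the two-sided 95% CI for collagenase minus surgery is above 6.

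**The concern.** This kind of analysis is meant to show how far the missing data must depart from missing-at-random before the conclusion changes. Higher PEM scores are worse. A non-inferiority claim is therefore most exposed when unobserved collagenase patients do worse than the model predicts and unobserved surgery patients do better. That combination lies inside the ±10 range the plan chose for each arm, yet it is not run.

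Shifts that differ by arm are not far-fetched here. Section 8.5.1 accepts that unblinded participants' preferences may influence a self-reported outcome. Section 8.2.1 expects surgery patients to wait substantially longer for treatment. One version of the analysis includes patients who withdrew before treatment.

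At stake is the robustness statement. A report could say that the claim survived every scenario up to ±10 when a combination within that range would have reversed it.

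**Working it through.** **Inputs.** SAP section 3: margin 6, SD 22, one-sided 2.5%, 90% power at a true difference of 0, 284 analysed per arm, 20% attrition, 710 in total. Section 4: 1:1 allocation, so 710/2 = 355 randomised per arm. Section 8.3.1: shifts up to ±10. Assumptions: equal missingness in the two arms, and a standard error not changed by the imputation.

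**Plan's own figures.** The normal approximation gives 2 × 22² × (1.960 + 1.282)² / 6² ≈ 283 per arm. The noncentral t calculation gives power 0.8995 at 283 and 0.9005 at 284, so 284 per arm (568) reproduces. 568/0.80 = 710 also reproduces.

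**Effect of a shift.** If a fraction m of an arm is missing and its mean is shifted by δ, that arm's mean moves by m × δ. The treatment difference therefore moves by m_C × δ_C - m_S × δ_S (C collagenase, S surgery).

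**At 20% missing per arm and an observed difference of 0.** SE = 22 × √(2/284) = 1.846; half-width = 1.96 × 1.846 = 3.62.

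| Scenario | Movement | Upper limit |
|---|---|---|
| No shift | 0 | 3.62 |
| Same shift in both arms | 0.20δ - 0.20δ = 0 | 3.62 |
| Worst planned row (+10 collagenase only, or -10 surgery only) | 0.20 × 10 = 2.0 | 5.62 |
| +10 collagenase and -10 surgery | 0.20 × 20 = 4.0 | 7.62 |

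Opposite shifts reach the margin at d = (6 - 3.62)/(2 × 0.20) = 5.95. A one-arm shift would need (6 - 3.62)/0.20 = 11.9, outside the planned range.

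**Dependence on the observed difference (20% missing).** Non-inferiority is declared for estimates below 6 - 3.62 = 2.38. Subtracting 2.0 and 4.0 gives cut-offs of 0.38 and -1.62. The last column is the probability of each band if the true difference is 0.

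| Observed difference | What overturns the claim | Probability |
|---|---|---|
| 0.38 to 2.38 | planned one-arm rows already do | about 32% |
| -1.62 to 0.38 | only opposite shifts do | about 39% |
| below -1.62 | neither does | about 19% |

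The remaining 10% of trials do not declare non-inferiority.

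**Dependence on attrition (observed difference 0, 355 randomised per arm).** The half-width is recomputed with 355 × (1 - m) analysed per arm.

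| Missing per arm | Half-width | Worst planned row | Opposite ±10 |
|---|---|---|---|
| 10% | 3.41 | 4.41 | 5.41 |
| 15% | 3.51 | 5.01 | 6.51 |
| 20% | 3.62 | 5.62 | 7.62 |
| 25% | 3.74 | 6.24 | 8.74 |

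At 10% neither crosses 6; at 25% both do.

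**Baseline adjustment.** The plan gives no baseline-outcome correlation. Assuming 0.5 to 0.7 at 20% missing and a difference of 0, the worst planned row gives 5.13 to 4.58 and opposite shifts give 7.13 to 6.58, so the pattern is the same.

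**The case against.** A reader might infer that the plan never examines the direction that threatens the claim, or that its grid cannot overturn non-inferiority. The SAP supports neither. The collagenase-only rows at +1 to +10 and the surgery-only rows at -1 to -10 all move the estimate towards inferiority, which makes 20 adverse rows. For observed differences of 0.38 to 2.38 at 20% missing, those rows already reverse the conclusion.

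Other objections have weight:

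- The shifts are additive, so a reader could rebuild an opposite-shift point estimate from the planned table: collagenase-only at +d, plus surgery-only at -d, minus the zero row. This is true, but it gives only an approximate confidence limit, and the table reports no tipping point.
- A +10/-10 pair is a 20-point gap between arms in the departure from missing-at-random, more than three times the margin. No passage shows that surgery non-responders would do better while collagenase non-responders do worse. How plausible the extreme is remains a judgement, which is why the tipping value matters more than the corner cell.
- The same-shift rows cancel only when missingness is equal. The SAP gives no rates by arm, and with unequal missingness these rows do carry information.
- The decision rests on the primary model. This analysis is supplementary, and no rule in the SAP declares robustness from it.

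These points limit the importance of the gap. They do not supply the missing combination.

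**Conclusion.** The point holds as an incomplete sensitivity analysis. It is not an error in the primary analysis, nor a contradiction in the plan. Within its own ±10 bounds the grid leaves out the least favourable pairing and, with equal missingness, reaches only half the adverse movement those bounds allow (2.0 against 4.0 points at 20% missing). At the result the trial is powered on, that separates an upper limit of 5.62 from one of 7.62, on opposite sides of the margin.

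The consequence is conditional. At 20% missing it matters for observed differences of about -1.62 to 0.38. If the true difference is 0, that band holds about 39% of trials, or 0.39/0.90 ≈ 43% of those that declare non-inferiority. At an observed difference of 0 the gap decides the outcome at 15% and 20% missing, but not at 10% or 25%.

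The exact limits rest on SD 22, equal missingness and a fixed standard error. The planned baseline adjustment, cluster-robust standard error and two analysis populations will change them.

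**What to change.** In section 8.3.1, state that the sensitivity parameter will also be applied with opposite signs: +d in collagenase with -d in surgery, and the reverse, for d = 1 to 10, in both versions of the analysis. Add the matching rows to the Appendix E-2 table. Report the smallest d at which the upper 95% limit exceeds 6, or state that none does up to 10.

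The one-arm rows already require arm-specific values, so this needs no new data, model or range. The cost is a few more runs, extra table rows and a less favourable reported worst case.

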### 8.3.2 Other sensitivity analyses of the primary outcome

In addition to the sensitivity analyses investigating the possible influence of missing data, a further three sensitivity analyses will be conducted, investigating the possible influence of differential delay between baseline and treatment delivery in each arm, deviations from the scheduled timing of post-treatment follow ups and an analysis adjusting for additional predictors of disease recurrence. The results of these analyses will be reported in a similar manner to the reporting of the primary analysis (Appendix E-2).

Delay between baseline and treatment delivery differs between the two arms, with participants in the surgery arm generally waiting longer between the two time points. The additional delay in the surgery

arm may lead to greater disease progression by the point of treatment delivery. Hence the baseline measurements in the surgery arm may underestimate severity of disease (at treatment) in comparison to those in the collagenase arm, meaning covariate adjustment using the baseline measurements may lead to a treatment effect estimate which is biased toward zero. Thus the treatment effect estimate from the model adjusting for baseline (as in the primary analysis) may be anti-conservative (in the context of non-inferiority). We will therefore supplement this estimate, with an estimate from a model which adjusts for the PEM measurement taken at treatment delivery (in place of the baseline measurement with all other terms remaining the same as the primary analysis). Any missing treatment delivery PEM scores will be imputed with predicted scores via regression of the observed treatment delivery PEM scores on observed baseline PEM scores and reference joint (MCP or PIP). If the baseline PEM score is also missing then the reference joint strata specific means will be used instead.

To investigate the robustness of the primary analysis to deviations from the scheduled timing of study visits/assessments, the primary analysis models will be refitted using only participants who had PEM scores collected within +/-14 days of the scheduled visit date at 3 and 6 months and within +/-91 days of the scheduled visit date at 12 and 24 months. Any missing baseline PEM scores will be imputed as for the primary analysis.

We will investigate whether the inclusion of additional baseline predictors of recurrence has any impact on the results of the primary analysis. The primary analysis model will be refitted including four additional predictors of recurrence collected at baseline; presence/history of bilateral disease (binary), presence/history of Garrods pads, Peyronie's disease or Ledderhose disease (binary), family history (binary) and age at which the patient first experienced Dupuytren's contracture (linear term). This analysis will be based on complete cases only.

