## **2. Design**

DISC is a multi-centre, parallel group, individually randomised controlled non-inferiority trial of collagenase injection and manipulation versus limited fasciectomy surgery for the treatment of Dupuytren's contracture. In addition to the main study, DISC contains a qualitative sub study and a photography sub study. This plan outlines the pre-specified analyses of the main trial and the photography sub study. Eligible and consenting patients will be randomised 1:1 to either collagenase injection and manipulation or limited fasciectomy surgery, using a secure randomisation service. Due to the nature of the interventions under investigation, it is not possible to blind clinicians or participants to their treatment allocation. Both treatments should be delivered within 18 weeks of randomisation (as per referral to treatment time), however where possible sites should deliver treatment within 12 weeks of randomisation. Participants will be followed up at 2 and 6 weeks post treatment and 3, 6, 12 and 24 months post treatment. A flow diagram illustrating the flow of participants through the study is presented in Appendix A.

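### Section 8.3.2 imputes missing treatment-delivery PEM scores without allocation, which restores a share of the bias this sensitivity analysis is meant to remove, roughly equal to the share missing

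*SAP*

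**What the plan says.** SAP Section 8.3.2 describes the delay from baseline to treatment as differing between arms, "with participants in the surgery arm generally waiting longer between the two time points". It reasons that the additional delay in the surgery "arm may lead to greater disease progression by the point of treatment delivery". Adjusting for baseline PEM, as the primary model does, could then be anti-conservative for non-inferiority. The planned check refits the primary model with the treatment-delivery PEM in place of the baseline PEM.

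Missing delivery scores are filled with predictions "via regression of the observed treatment delivery PEM scores on observed baseline PEM scores and reference joint (MCP or PIP"). If baseline PEM is missing too, the mean for the reference-joint stratum is used. Allocation, waiting time and separate fitting by arm are not mentioned in either rule, so as written both are pooled over arms.

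Section 8.3.1 treats the same variable differently. Table 3 lists the treatment-delivery PEM in the multiple imputation model, and that imputation is run separately by randomised group.

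**The concern.** Leaving allocation out of an imputation model is sound for a true baseline covariate, because randomisation makes it independent of arm. That is the case for the baseline PEM in the primary model. The delivery score is different: it is measured after randomisation, and the analysis exists because it may differ by arm.

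A pooled prediction carries an average of the two arms' progression. If surgery patients do progress more while waiting, those with a missing delivery score get a value that is too low, and collagenase patients with a missing score get one that is too high. The covariate then under-corrects. Higher PEM is worse and the treatment difference is collagenase minus surgery, so the leftover bias is negative: it favours collagenase, the direction the SAP warns about. To that extent the check would sit closer to the primary result than it should.

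**Working it through.** **Inputs from the SAP.** Section 3 sizes the trial "assuming a non-inferiority margin of 6 points and a standard deviation of 22 points", using a "one-sided independent samples t-test of size 2.5"%. It states: "An effective sample size of 568 participants (284 per arm) is required to obtain 90% power". It adds: "Assuming 20% attrition at the 12 month follow up, the total target sample size is 710". The SAP gives no figure for the progression gap, the fraction of delivery scores missing, or the slope of 12-month PEM on delivery PEM. All three are assumptions below.

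**The SAP's own figure.** The normal approximation, 2 × 22² × (1.960 + 1.282)² / 6², gives 283 per arm. With the exact noncentral t, power is 0.8995 at 283 and 0.9005 at 284 per arm, so 284 (568 in total) is right. 568 / 0.8 = 710. Both figures reproduce. The standard error implied by the same inputs is 22 × √(2/284) = 1.85 points, and the 95% CI half-width is about 3.6.

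**Formula.** Let D be the extra progression in surgery before treatment, m_S and m_C the missing fractions in surgery and collagenase, p the surgery share of the observed delivery scores, and β the slope of outcome on delivery PEM.

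- The pooled prediction is too low by (1 − p)D in surgery and too high by pD in collagenase.
- The between-arm gap in the filled-in covariate is D[1 − m_S(1 − p) − m_C p].
- Residual bias in the treatment difference = −βD[m_S(1 − p) + m_C p]. With equal missingness m this is −βDm.
- Baseline adjustment has bias −βD, so the share restored is m.

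**Results for β = 0.6, equal missingness (points):**

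| Missing | D = 2 | D = 4 | D = 6 | D = 8 |
|---|---|---|---|---|
| 5% | -0.06 | -0.12 | -0.18 | -0.24 |
| 10% | -0.12 | -0.24 | -0.36 | -0.48 |
| 20% | -0.24 | -0.48 | -0.72 | -0.96 |
| 30% | -0.36 | -0.72 | -1.08 | -1.44 |

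Under baseline adjustment the bias is -1.2, -2.4 and -3.6 for D = 2, 4 and 6. The figures scale with β, so a slope of 0.3 would halve them all.

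Unequal missingness: with m_S = 20% and m_C = 5%, p = 0.80 / (0.80 + 0.95) = 0.457. The share restored is 0.20 × 0.543 + 0.05 × 0.457 = 0.131. At D = 4 the bias is -0.6 × 4 × 0.131 = -0.32.

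**Simulation check.** 2,000 trials per setting, 568 participants, 12-month ANCOVA, baseline-to-delivery correlation 0.7, true difference 6. At D = 4 and 20% missing:

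| Covariate | Bias | False non-inferiority |
|---|---|---|
| Delivery PEM, complete | -0.07 | 2.45% |
| Delivery PEM, pooled imputation | -0.55 | 5.35% |
| Delivery PEM, imputation with allocation | -0.06 | 2.35% |

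The pooled rule is -0.48 below the complete-data result, as the formula predicts. A separate simulation (baseline SD 20, 284 per arm, same slope) gave -0.3, -0.6 and -0.9 for D = 5 at 10%, 20% and 30% missing, and -0.5, -1.0 and -1.5 for D = 8. Adding allocation gave 0.0 throughout.

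**The case against.** The mechanism is hard to dispute, but its size is open to challenge, and most of that challenge stands.

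- **Nothing in the SAP points to a large missing fraction.** Section 7.2.1 has the pre-treatment form completed at the treatment visit, and Appendix B marks PEM at treatment delivery as mandatory. Section 8.1 limits the model to participants with a post-treatment score. The 20% attrition in Section 3 refers to 12 months, not to this visit. Higher missingness is not excluded, but low values have to be shown.
- **The progression gap may be small.** Section 8.3.2 says only that delay may lead to more progression. A gap of 8 points exceeds the 6 points that Section 3 calls relevant to patients.
- **At low missingness the effect is slight.** At 5% missing, 0.06 to 0.24 points is 0.03 to 0.13 of the 1.85-point standard error.
- **The SAP will show the ingredients.** Appendix E-2 tabulates pre-treatment PEM by arm with its N, and the unadjusted pre-treatment difference.
- **The zero bias after the fix is partly built in.** The simulated data follow the same linear model as the imputation. If missingness depends on the delivery score itself, neither rule is protected.

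One possible defence fails. The by-arm multiple imputation in Section 8.3.1 does not replace this check, because the imputed datasets are analysed with the primary model, which adjusts for baseline PEM.

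A reader might infer that the check is worthless, or that it loses a sixth of the margin. The documents support neither. At 10% missing about 90% of the bias is still removed. A loss of about one point is reached only towards the corner of the grid, with 20% or more missing and a gap of 6 to 8 points.

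**Conclusion.** The imputation rule in Section 8.3.2 is wrong as written for this covariate, and nothing else in the SAP repairs it. It restores a share of the differential-progression bias about equal to the fraction of delivery scores missing, in the anti-conservative direction.

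The direction follows from the SAP's own reasoning, provided progression really is greater in surgery. The size does not: it rests on an assumed slope of 0.6, gaps of 2 to 8 points and missing fractions of 5% to 30%. Over that range it runs from negligible to about a quarter of the margin (1.5 / 6), and 10% missing or less keeps it at half a point or below.

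It would be tempting to conclude that the non-inferiority decision is compromised. It is not: Section 8 rests that decision primarily on the primary analysis model, and Section 8.3.2 only supplements it. This is a modest flaw, worth correcting because the analysis is the stated check on a bias the SAP itself identifies.

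**What to change.** In Section 8.3.2, add randomised allocation to the regression that predicts missing treatment-delivery PEM, or fit that regression separately by arm, in line with the by-arm imputation in Section 8.3.1. Replace the fallback with means by reference joint and arm; it applies only when both scores are missing, so it will rarely matter. Time from randomisation to treatment can be added as an optional predictor, but allocation alone removed the bias in the simulations.

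The cost is one extra term and a reworded sentence. No new data are needed, the regression does not use the outcome, and if the arms do not differ in progression the added term costs essentially nothing. Reporting the fraction of delivery scores imputed in each arm beside the result would let readers judge how much rests on imputation.

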### **8.2.1 PEM completion**

Participants randomised to surgery will tend to wait substantially longer between baseline and treatment delivery. Hence we expect the data to show some degree of systematic imbalance with respect to time elapsed since baseline. The possible influence of this differential delay has been accounted for by referencing the follow-up data collection to the point of treatment delivery. Any changes in the primary outcome between baseline and treatment delivery due to natural progression of the disease are captured by inclusion of a measurement of the primary outcome at treatment delivery. Between group differences in the timing of treatment and follow up will be explored using tabular and graphical summaries as follows:

- A table of the time elapsed between randomisation and PEM completion at each time point by trial arm.
- Plots of time elapsed between randomisation and PEM completion at treatment delivery
- A table summarising the time elapsed between treatment and PEM completion at each post treatment time point (by trial arm), including the proportion of participants completing the PEM within the windows for completion specified in the protocol (+/- 14 days at 3 and 6 months, +/- 3 months at 12 and 24 months).
- Box plot of time elapsed between treatment and PEM completion at 12 months by trial arm.

We will also report the number/proportion of returned participant questionnaires and the number/proportion for which a valid score for the primary outcome could be calculated, as well as a summary of the different patterns of missingness and the frequency with which they occur. Templates of tables described in this section are given in Appendix E-1.

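### SAP 8.3.2 and Appendix E-2 define the follow-up-window sensitivity analysis differently, both in the unit restricted and in an 18-week pre-treatment condition that appears only in the table footnote

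*SAP*

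**What the plan says.** Section 8.3.2 introduces this analysis as one about "deviations from the scheduled timing of post-treatment follow ups", and repeats the purpose where it specifies it: "To investigate the robustness of the primary analysis to deviations from the scheduled timing of study visits/assessments". The rule is that "the primary analysis models will be refitted using only participants who had PEM scores collected within +/-14 days of the scheduled visit date at 3", with the same window for the 6-month visit. A further condition is joined to it for the later visits: "within +/-91 days of the scheduled visit date at 12 and 24 months". It contains no pre-treatment or 18-week condition.

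In Appendix E-2 the corresponding row is labelled "Sensitivity analysis using data collected within planned follow up window". Its asterisk leads to a footnote of timeframes that begins "Pre-treatment PEM completed within 18 weeks of randomisation, month 3 and month 6 PEM completed within +/-14 days of 3 and 6 months post treatment" and then gives three months either side at 12 and 24 months.

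Four other parts of the SAP bear on this:

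- Section 8.1 counts anyone with at least one post-treatment PEM score as part of the primary analysis.
- Section 8.2.3 uses the four post-treatment scores as outcomes and the baseline score as a covariate. The pre-treatment score has no place in the model.
- Section 8.2.1 lists the protocol's PEM windows for the four post-treatment visits only, and states: "Participants randomised to surgery will tend to wait substantially longer between baseline and treatment delivery".
- Section 2 sets 18 weeks from randomisation as the outer target for treatment in both arms.

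**The concern.** Two analysts following this document could build different datasets. One, working from 8.3.2, would keep or drop whole participants. The other, working from the table label, would keep or drop individual scores. The footnote offers a third version, with a filter on time to treatment.

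The choice affects what the result means. Under the literal 8.3.2 rule, someone whose 3-month PEM came 15 days late, or who has no 24-month PEM, loses a 12-month score collected exactly when due. The 18-week condition would exclude people on a post-randomisation variable that the SAP itself expects to differ by arm and, in 8.3.2, links to possible disease progression before treatment. A shift in the estimate or a wider interval could then reflect selection or lost precision as well as visit timing.

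**Working it through.** **The two definitions side by side**

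| Feature | Section 8.3.2 | Appendix E-2 |
|---|---|---|
| Unit restricted | participant | data (row label) |
| 3 and 6 months | 14 days either side | 14 days either side |
| 12 and 24 months | 91 days either side | 3 months either side |
| Pre-treatment PEM | no condition | within 18 weeks of randomisation |

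The 91-day and 3-month wordings agree for practical purposes (365.25/4 = 91.3 days). The first and last rows do not agree. Because the refitted model uses the pre-treatment PEM neither as outcome nor as covariate, the 18-week condition can change the result only by removing participants.

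**The SAP's planning figure**

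Inputs from section 3: margin 6, SD 22, one-sided 2.5%, power 90%, true difference 0.

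- Normal approximation: n per arm = 2 × 22² × (1.96 + 1.2816)² / 6² = 282.5, so 283.
- With the t distribution, 283 per arm gives 89.95% power and 284 gives 90.05%. So 284 per arm (568) reproduces.
- 568 / 0.80 = 710 also reproduces.

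**What each rule would cost (illustration)**

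The SAP gives no in-window rates. Assume 284 per arm, SD 22, no gain from baseline adjustment or repeated measures, and a probability w that the score at each visit is present and in window, independently across visits. The score-level rule keeps 284w 12-month scores per arm. The all-four rule keeps 284w⁴ participants per arm. The 95% half-width is 1.96 × 22 × √(2/n), which is 3.62 at n = 284. Power is from the two-sample t-test at true difference 0.

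| w | Score-level n per arm | Half-width | Power | All-four share (w⁴) | All-four n per arm | Half-width | Power |
|---|---|---|---|---|---|---|---|
| 0.95 | 270 | 3.71 | 88.5% | 81.5% | 231 | 4.01 | 83.3% |
| 0.90 | 256 | 3.81 | 86.8% | 65.6% | 186 | 4.47 | 74.7% |
| 0.80 | 227 | 4.05 | 82.7% | 41.0% | 116 | 5.66 | 54.4% |
| 0.70 | 199 | 4.32 | 77.4% | 24.0% | 68 | 7.40 | 35.2% |

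Independence matters. Punctuality is probably positively correlated within a person, which raises the share kept under the all-four rule. With the same w at every visit that share cannot exceed w, so at w = 0.90 it lies between 66% (independent) and 90% (the same people punctual every time).

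**Adding the 18-week condition (illustration)**

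The SAP gives only the direction of the difference in waiting. At w = 0.90 under the all-four rule (186 per arm), with assumed shares treated beyond 18 weeks:

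| Beyond 18 weeks, collagenase / surgery | n kept, collagenase / surgery | Power | Share of those removed who are surgery |
|---|---|---|---|
| 5% / 5% | 177 / 177 | 72.5% | 50% |
| 5% / 20% | 177 / 149 | 68.7% | 80% |
| 5% / 40% | 177 / 112 | 61.4% | 89% |

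If the 18-week target is met in both arms, the condition removes almost no one.

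**The case against.** The best defence is that 8.3.2 can be read visit by visit. It never says that all four scores are required. The table label points to data, the row reports separate estimates at each visit, the primary model accepts anyone with one score, and the SAP says so outright where it wants complete cases (the diathesis analysis at the end of 8.3.2, and 8.4.1 and 8.4.2). The footnote lists timeframes and does not state an exclusion rule. The tables planned in 8.2.1 and Appendix E-1 show, by arm, the time to each PEM and the number in window, so a reader would see differential waiting and compliance beside the result. Most of this stands. It makes the unit of restriction inconsistent rather than settled, but does not remove the inconsistency: the literal text and the table still give different datasets, and the footnote is tied to this one row.

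A reader might infer more than the document supports:

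- **That the 18-week condition removes mainly surgery participants.** The direction follows from section 8.2.1. No waiting times are given, and 18 weeks is the target in both arms, so the number could be small.
- **That the analysis no longer tests visit timing.** The window restriction applies under either reading; timing would be mixed with selection, not replaced by it.
- **That the upper limit could pass 6 through lost precision alone.** That needs rates the SAP does not give. At an observed difference of 1 the half-width must exceed 5, so retention must fall below (3.62/5)² = 52%. At a difference of 0 it must fall below (3.62/6)² = 36%. With four independent visits these correspond to w below about 85% and 78%.

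**Conclusion.** The point holds as a text-and-table inconsistency in one supportive analysis, with a better rule available. Followed literally, 8.3.2 discards usable 12-month primary scores because of events at other visits. If the footnote is applied, it adds an exclusion on waiting time that lies outside the analysis's stated purpose and would probably fall more on the surgery arm. The result would combine visit timing with selection on completeness and, possibly by arm, on waiting time.

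The size cannot be fixed from the SAP. At an assumed 90% in window per visit, independent across visits, the contrast is about 90% of 12-month scores kept against about 66% of participants. Positive correlation between visits would narrow that gap. The effect of the 18-week condition ranges from negligible upwards. Non-inferiority is judged primarily on the primary model's confidence interval (section 8), so the primary decision is unaffected.

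**What to change.** In 8.3.2, and in matching words in Appendix E-2, state that:

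- any individual post-treatment PEM score more than 14 days from its due date at 3 or 6 months, or more than 91 days at 12 or 24 months, is set to missing;
- the participant's in-window scores are retained;
- the primary model is refitted under its existing missing-at-random assumption.

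Remove the 18-week condition from this row's footnote. If a restriction on time to treatment is wanted, specify it as a separate analysis with exclusions reported by arm. Section 8.3.2 already addresses differential delay by adjusting for the PEM at treatment delivery.

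The cost is a sentence or two and one footnote, with no new data. The remaining limitation is that setting late scores to missing still selects on visit timing and relies on missing at random, so the report should say so and give the number of scores removed by arm and visit.
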